9.1 Thirty (30) Day Follow-Up Evaluation

An evaluation will be scheduled for 30 day follow-up (±7 days). The following assessments will be performed:

- Medical History
- NYHA Class
- Cardiovascular Medications
- Targeted Physical Exam
- 12-lead ECG
- Transthoracic Echocardiography
- NT-Pro-BNP or BNP
- Kansas City Cardiomyopathy Questionnaire (KCCQ)
- SF-36v2 Health Survey (SF-36)
- 6 Minute Walk Test (6MWT)
- Continued Activity Monitoring data collection from baseline to the 180 day follow-up. The patient should be wearing the activity monitor wrist watch at time of the 30 day follow-up visit.
- Neurological Assessments:

Neurological Assessment will be conducted by a neurologist, a neurology fellow, or designee. Every effort should be made to have a neurologist or neurology fellow perform the neurological assessments, or alternatively, a trained research team member certified in stroke assessment, which consist of:

- NIHSS
- Modified Rankin Scale (mRS): mRS can be obtained by a certified research team member via phone interview with the patient or caregiver member if the patient is unable to visit the research office.
- Adverse Events

If the patient reports any adverse events that are potentially serious during the follow-up period, the patient should return to the investigator's facility for further evaluation of the event.

9.2 One Hundred Eighty (180) Day Follow-Up Evaluation

An evaluation will be scheduled for 180 day follow-up (± 14 days). The following assessments will be performed:

- Medical History
- NYHA Class
- Cardiovascular Medications
- Targeted Physical Exam
- 12-lead ECG
- Transthoracic Echocardiography
- Complete blood count (no WBC differential necessary)
- Chemistry panel
- NT-Pro-BNP or BNP
- Kansas City Cardiomyopathy Questionnaire (KCCQ)
- SF-36v2 Health Survey (SF-36)
- 6 Minute Walk Test (6MWT)
- Neurological Assessments

Neurological Assessments will be conducted by a neurologist, a neurology fellow, or designee. Every effort should be made to have a neurologist or neurology fellow perform the neurological assessments, or alternatively, a trained research team member certified in stroke assessments, which consist of:

- NIHSS
- Modified Rankin Scale (mRS): mRS can be obtained by a certified research team member via phone interview with the patient or caregiver member if the patient is unable to visit the research office.
- Continued Activity Monitoring data collection from baseline to the 180 day follow-up.
 - At the 180 day follow-up visit, the patient will return the Activity Monitoring Devices.
 If a patient's daily wear compliance rate (minimum 8 hours between 6am to 10pm) is
 less than 50% in the 30 days prior to the visit, an additional month (30 days) of Activity
 Monitoring will be completed. Devices will be returned following the month of Activity
 Monitoring.
- Adverse Events

PROTOCOL NUMBER: 2017-05

If the patient reports any adverse events that are potentially serious during the follow-up period, the patient should return to the investigator's facility for further evaluation of the event.

9.2.1 Primary Endpoint Compliance

In order to ensure completeness of the primary endpoints at 12-month study visit, the investigational sites are advised to schedule the visit as early in the window (+/- 45 days) as possible to ensure compliance in the event a visit needs to be rescheduled for any reason.

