5.2 Primary Safety Endpoint (Evaluated through 30 Days post procedure) [Device Group only]

Overall rate of device and procedure related Major Adverse Events (MAEs) through 30 days post-procedure (including death, stroke, myocardial infarction, pericardial effusion requiring drainage, left circumflex coronary artery injury requiring intervention, mitral valve reintervention and access site and vascular complications requiring intervention. The primary safety endpoint was chosen to detect any concerns relating to safety of the Edwards Cardioband System implantation procedure.

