Both patients were hospitalized** equal number of times	Go to Step 3
Step 3	
If no ranking yet available	
Patient in Device group but not patient in Control group	Favors Device
improved 6 minutes walking distance ≥ 40 meters compared to	
baseline	
Patient in Control group but not patient in Device group	Favors Control
improved 6 minutes walking distance ≥ 40 meters compared to	
baseline	
Both patients improved 6 minutes walking distance ≥ 40	Go to step 4
meters compared to baseline	
Neither of the patients improved 6 minutes walking distance ≥	Go to step 4
40 meters compared to baseline	
Step 4	
If no ranking yet available	
Patient in Device group (but not control) improved KCCQ score	Favors Device
≥10 points compared to baseline	
Patient in control group (but not device)improved KCCQ score	Favors Control
≥10 points compared to baseline	
Both patients improved KCCQ score ≥10 points compared to	Tie
baseline	
None of the patients improved KCCQ score ≥10 points	Tie
compared to baseline	

^{**} Only hospitalizations for heart failure are counted

The following rules are applied with the pairwise comparative outcome assessment:

- If any one of the patients in a patient pair is missing data for a variable included in the hierarchy then the pair will be considered a tie in regards to that variable/level and will proceed to the next level in the hierarchy.
- The time dependent events are censored at exactly 1 year after randomization.
- Patients who are censored during the first year (includes patients who are lost to follow-up as well as patients who die) will be compared to other patients using available data up until the time at which the patient was censored. In other words,

PROTOCOL NUMBER: 2017-05

the number of heart failure hospitalizations up until the censoring time will be compared between the patient pair.

- Inclusion of hospitalizations is based on adjudication by the Clinical Events Committee (CEC).
- The index hospitalization for Edwards Cardioband System implant in patients randomized to Device group is not counted as heart failure related hospitalization. However, if the hospital stay is prolonged beyond 5 days because of a heart failure complication, it is counted as a HF-related hospitalization. This rule is also applies to surgical mitral annuloplasty or replacement that are performed during follow-up in patients randomized to Control.

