- Hospitalizations beginning prior to the exact 1 year time point are counted for analysis of frequency of hospitalization.
- The 6MWT and KCCQ data from the 1-year visit are used regardless of whether the visit is before or after the exact 1 year time point.
- If clinical follow-up of one or both patients is censored, the pairwise outcome assessment is performed on the basis of those events that occurred during the smaller of the two follow-up times. Specifically, if a Control patient experiences an event on a particular day, and the Device patient is censored on that day or a later day, then the pair favors Device.

Details of the pairwise comparative outcome assessment process with full scenario analyses are provided in the Statistical Analysis Plan (SAP).

The Finkelstein-Schoenfeld test statistic is a Generalized Gehan Wilcoxon (GGW) test that requires information about the pairwise outcome assessment of all pairwise comparisons, including those within the Device and Control groups.²⁹

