### 5. **DEFINITIONS**

### 5.1 Analysis Dates and Days

- Study start date is defined as the procedure date.
- Last information date is defined as the most recent date assessed with any available information concerning the patient (e.g., most recent date out of: baseline assessment, procedure, discharge, follow-up visits, laboratory tests, study termination, and adverse events). Last information date is used as censor date for survival analyses.
- Study day = Date Study start date

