### 5.2 Visit Windows

Assessments are considered by their nominal visit name (e.g., "30 days" and "1 year") regardless of whether the actual visit date is within the protocol defined visit window.

- 30 Days: Day 23 Day 37
- 6 Months: Day 166 Day 194
- 1 Year: Day 320 Day 410
- 2 Years: Day 670 Day 790
- 3 Years: Day 1035 Day 155
- 4 Years: Day 1400 Day 1520
- 5 Years: Day 1765 Day 1885

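### Sites are advised to hold the 1-year visit from day 320, but events count to a full year and no status check closes the gap, so late follow-up can depend on having an event

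*Protocol*

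**What the plan says.** **Visit timing.** Protocol 9.2.1 states that "sites are advised to schedule the visit as early in the window (+/- 45 days) as possible", to leave time for rescheduling. SAP 5.2 gives the window as "1 Year: Day 320 Day 410". The next visit with an adverse-event assessment is the 2-year visit (Protocol 9.4), on day 670 at the earliest. Device visits run from the procedure and Control visits from randomization (Protocol section 9). Randomization may precede the procedure by up to 14 days (Protocol section 4).

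**Event window.** For co-primary endpoint II, Protocol 13.4.2 says: "The time dependent events are censored at exactly 1 year after randomization". It adds: "Hospitalizations beginning prior to the exact 1 year time point are counted for analysis of frequency of hospitalization". Under Protocol 13.4.4, secondary HF hospitalizations run from day 0 to day 365 post procedure, and cardiovascular and all-cause mortality run up to 365 days. Stroke, TIA, vascular and renal outcomes run through 1 year (Protocol 5.8).

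**Censoring.** SAP 5.1 says: "Last information date is used as censor date for survival analyses". The dates that can supply that last information include visits, laboratory tests, study termination and adverse events. SAP 6.1 censors patients without events at the last time they were known to be event-free. In the Finkelstein-Schoenfeld comparison, if a patient is censored, "the pairwise outcome assessment is performed on the basis of those events that occurred during the smaller of the two follow-up times".

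**The concern.** The early-visit advice suits echo, 6MWT and KCCQ, which are measured at the visit. It does not suit outcomes that accrue to a fixed date, because an early visit cannot confirm what happens after it. Two things are at stake.

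- **Completeness.** After the visit, an event enters the database only if the site hears of it. Absence of an event is not confirmed until the 2-year visit, which many patients may not have reached at primary lock. SAP 8.10 treats data from completed patients as fixed in the sample size re-estimation, so the same gap would carry into that step.
- **Bias.** A patient seen on day 320 with no later record can be censored that day, while one with a reported event on day 340 is followed to day 340. Length of follow-up then depends on outcome, which log-rank, Kaplan-Meier and intensity-model analyses assume it does not.

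**Working it through.** **1. The plan's power figure.** The Finkelstein-Schoenfeld test was simulated with the SAP variance, the inputs of Protocol 13.5, 200 Device and 100 Control patients, and full follow-up to day 365. Power was 94.7% with deaths at constant hazard and 93.4% with deaths spread evenly over the year. This agrees with the synopsis (above 90%). It does not reproduce the 87% that Protocol 13.5 and SAP 8.11 give on the same inputs, and those figures need reconciling separately.

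**2. Length of the gap, for visits inside the window.**
- Control: 365 − 320 = 45 days, and 45/365 = 12.3% of the year.
- Device, on the randomization clock: a procedure 14 days after randomization puts the earliest visit on day 334, and 365 − 334 = 31 days. A same-day procedure gives 45. The range is 31 to 45 days.
- Secondary HF hospitalizations count from the procedure, so the Device gap there is up to 45 days.
- From day 365 to the earliest 2-year visit: 670 − 365 = 305 days.

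**3. Events expected in the gap** (375 patients, 250 Device and 125 Control, every visit on its earliest day).
- Deaths, 20% at 1 year, constant hazard. For 45 days: 0.8^(320/365) − 0.8 = 0.0223, and × 375 = 8.4 of 75. Evenly spread deaths give 0.2 × 45/365 × 375 = 9.2.
- With a 31-day Device gap: (0.8^(334/365) − 0.8) × 250 = 0.0153 × 250 = 3.8. Adding Control, 0.0223 × 125 = 2.8, gives 6.6.
- HF hospitalizations per patient, taking five or more as 5. Control: 0.1 + 0.2 + 0.3 + 0.2 + 0.25 = 1.05. Device: 0.1 + 0.1 + 0.15 + 0.2 + 0.25 = 0.80. Year totals: 131.25 + 200 = 331.25.
- Spread evenly, Control has 131.25 × 45/365 = 16.2 in the gap. Device has 200 × 45/365 = 24.7, or 200 × 31/365 = 17.0. The total is 33 to 41 of 331.
- Strokes cannot be sized, because the plan gives no rate.

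**4. What censoring could do: two limiting cases in Control.** On the plan's rate, 125 × 0.8223 = 103 patients are alive on day 320 and about 3 of them die by day 365. Suppose all are seen on day 320 and no survivor has a later dated record.
- If no late death is reported, the estimate labelled 1-year mortality is 1 − 0.8223 = 17.8%, not 20%.
- If all late deaths are reported, each extends that patient's follow-up. Only about 3 patients remain in the risk set at the first late death, and the Kaplan-Meier curve then falls to zero.

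Neither extreme is expected. They show that the two errors run in opposite directions, so the net direction cannot be assumed.

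**5. Power with early closure** (300 patients, constant hazard).

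| Follow-up closed at | Power |
|---|---|
| Day 365 for all | 94.7% |
| Day 320 for all | 96.5% |
| Device day 334, Control day 320 | 96.3% |
| Uniform over days 320 to 365 | 95.8% |

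Power does not fall. Mortality is assumed equal in the two groups, and a shorter window lets that neutral top tier decide fewer pairs. These runs close follow-up at the visit for everyone and do not model follow-up extended by events, so they do not address bias.

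**The case against.** **The other side.** Adverse events are collected from consent to exit (Protocol 6.6). Death and inpatient hospitalization are serious adverse events, due within 3 calendar days of the site learning of them (Protocol 11.2, 11.5.3, 11.6), and HF hospitalizations are adjudicated. The early-visit advice is a deliberate trade: it protects MR, 6MWT and KCCQ, which are not imputed in the primary analysis. The dates in SAP 5.1 are examples, and the month of activity monitoring after the 1-year visit could supply dated information to about day 350. SAP 6.1 sends patients to last-follow-up censoring when they have not completed the analysis visit, and an early-visit patient has completed it.

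**What stands of it.** Reporting is real but passive: it can record an event and cannot confirm that none occurred. Activity monitoring is optional and is not an event check. The death-index search in Protocol 12.3 is for losses to follow-up, and a patient seen on day 320 is not lost. SAP 6.1 still censors event-free patients at their last known event-free time.

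**Stronger readings that the documents do not support.**
- A reader might infer that late first-year events go unobserved. Continuous reporting and the 2-year visit can both capture them.
- A reader might infer that the Finkelstein-Schoenfeld pairs will discard reported late events. That follows only if the SAP 5.1 date is used in the pairs. SAP 5.1 speaks of survival analyses, while the pairwise section has its own rule of censoring at exactly 1 year and names losses to follow-up and deaths as the earlier censorings. The text leaves this open.
- A reader might infer that primary safety ("Overall rate of device and procedure related Major Adverse Events (MAEs) through 30 days") has the same fault, since the visit may fall on day 23. The early-visit advice does not cover that visit, the analysis is a rate with a confidence interval, and the 180-day visit asks about adverse events again. That point is minor.

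**Conclusion.** The concern holds as a gap in ascertainment and an unclear censoring rule. Early visits are encouraged, the event window stays open for up to 45 more days, and no scheduled contact closes it before the 2-year visit. Under SAP 5.1 and 6.1, follow-up in that gap can depend on having an event. If the same date governs the Finkelstein-Schoenfeld pairs, reported late events could also be dropped from pairs with an early-visit patient.

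The upper bound is about 8 of 75 deaths and 41 of 331 HF hospitalizations. It assumes every visit on day 320, a 45-day Device gap, constant hazard for death, evenly spread hospitalizations, and none of these events reported before lock. With procedures 14 days after randomization it falls to about 7 deaths and 33 hospitalizations. The actual loss depends on visit dates, reporting and the lock date, and the documents available do not allow it to be placed within the bound. A reader might infer a loss of power, but none is shown; the size and direction of any bias are unknown.

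**What to change.** 1. Keep the early 1-year visit for echo, 6MWT and KCCQ.
2. In Protocol 9.2.1 and 9.3, add a telephone or record check of vital status, hospitalizations and adverse events on or after day 365 from randomization for every patient seen earlier, completed before primary lock. Where an analysis counts from the procedure, the check must also reach day 365 on that clock.
3. In SAP 5.1, set the censor date to the last complete event-status contact, so that an adverse-event report alone does not extend follow-up. State that this date applies to the Finkelstein-Schoenfeld pairs.
4. Minor: where the 30-day visit falls before day 30, confirm major adverse event status through day 30 by a contact or at the 180-day visit.

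The cost is one short call or record check per patient seen early, slight site workload, and wording changes in both documents. No extra clinic visit or procedure is needed.

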9.3 One (1) Year Follow-Up Evaluation

An evaluation will be scheduled for the 1 year follow-up (± 45 days). The following assessments will be performed:

- Medical History
- NYHA Class
- Cardiovascular Medications
- Targeted Physical Exam
- 12-lead ECG
- Transthoracic Echocardiography
- CBC (no WBC differential necessary)
- Chemistry panel
- NT-Pro-BNP or BNP
- Kansas City Cardiomyopathy Questionnaire (KCCQ)
- SF-36v2 Health Survey (SF-36)
- 6 Minute Walk Test (6MWT)
- Adverse Events

If the patient reports any adverse events that are potentially serious during the follow-up period, the patient should return to the investigator's facility for further evaluation of the event.

Neurological Assessments

PROTOCOL NUMBER: 2017-05

Neurological Assessments will be conducted by a neurologist, a neurology fellow, or designee. Every effort should be made to have a neurologist or neurology fellow perform the neurological assessments, or alternatively, a trained research team member certified in stroke assessment, which consist of:

- NIHSS
- Modified Rankin Scale (mRS): mRS can be obtained by a certified research team member via phone interview with the patient or caregiver member if the patient is unable to visit the research office.
- Activity Monitoring data collection will be restarted at the time of the 1 year visit. The
 patient will be provided Activity Monitoring devices and following a month (30 days) of
 data collection will be instructed to return the device.

9.4 Two (2) Year Follow-Up Evaluation

An evaluation will be scheduled for the 2 year follow-up (± 60 days). The following assessments will be performed:

- Medical History
- NYHA Class
- Cardiovascular Medications
- Targeted Physical Exam
- Transthoracic Echocardiography
- NT-Pro-BNP or BNP
- Kansas City Cardiomyopathy Questionnaire (KCCQ)
- SF-36v2 Health Survey (SF-36)
- 6 Minute Walk Test (6MWT)
- Adverse Events

If the patient reports any adverse events that are potentially serious during the follow-up period, the patient should return to the investigator's facility for further evaluation of the event.

Neurological Assessments

Neurological Assessments will be conducted by a neurologist, a neurology fellow, or designee. Every effort should be made to have a neurologist or neurology fellow perform the neurological

PROTOCOL NUMBER: 2017-05

assessments, or alternatively, a trained research team member certified in stroke assessment, which consist of:

- NIHSS
- Modified Rankin Scale (mRS): mRS can be obtained by a certified research team member via phone interview with the patient or caregiver member if the patient is unable to visit the research office.

9.5 Three (3) to Five (5) Year Annual Follow-Up Evaluations (± 60 days)

The following assessments will be performed on an annual basis at three, four and five years (±60 Day):

- Medical History
- NYHA Class
- Cardiovascular Medications
- Targeted Physical Exam
- Transthoracic Echocardiography
- NT-Pro-BNP or BNP
- Kansas City Cardiomyopathy Questionnaire (KCCQ)
- SF-36v2 Health Survey (SF-36)
- Adverse Events

If the patient reports any adverse events that are potentially serious during the follow-up period, the patient should return to the investigator's facility for further evaluation of the event.

Neurological Assessments

Neurological Assessments will be conducted by a neurologist, a neurology fellow, or designee. Every effort should be made to have a neurologist or neurology fellow perform the neurological assessments, or alternatively, a trained research team member certified in stroke assessment, which consist of:

- NIHSS
- Modified Rankin Scale (mRS): mRS can be obtained by a certified research team member via phone interview with the patient or caregiver member if the patient is unable to visit the research office.

PROTOCOL NUMBER: 2017-05

9.6 Study Exit

If the patient exits the study prior to completing the required assessments, the Study Exit CRF must be completed.

10 Schedule of Study Visits and Patient Assessments

Evaluation of patients enrolled in this study will include all tests and procedures listed in the Schedule of Study Visits and Patient Assessments as outlined in Table 4.

PROTOCOL NUMBER: 2017-05

Table 4: Schedule of Study Visits and Patient Assessments

Test/ Assessment	Screening/ Baseline	Random -ization	Pre-Index Procedure- Edwards Cardioband System (Device group only; timing: per local institutional standard of care)	Index Procedure- Edwards Cardioband System (Device group only)	Post- Edwards Cardioband System Procedure, Pre- Discharge (Device group only)	30 Day F/U (±7 days)	180 Day F/U (± 14 days)	1 Year F/U (±45 days)	2 Year F/U (± 60 days)	3, 4, 5 Year F/U (± 60 days)
Study Visit No.	1	3	4	5	6	7	8	9	10	11, 12, 13
Study Consent	X									
Medical Hx/ NYHA Class	X					Х	Х	Х	Х	Х
STS Score	X									
Cardiovascular Medications	X			X	Х	X	X	Х	X	Х
Targeted Physical Exam	Х					Х	Х	Х	Х	Х
12-Lead ECG	Х				Х	Х	Х	Х		
Transthoracic Echo (TTE)	Х				Х	Х	Х	Х	Х	Х
Transesophageal Echo (TEE)	X			Х						
Cardiac CT Imaging	X									
Randomization		Х							_	
Pregnancy Test (for females of childbearing potential only)	X ¹		X							

PR

Test/ Assessment	Screening/ Baseline	Random -ization	Pre-Index Procedure- Edwards Cardioband System (Device group only; timing: per local institutional standard of care)	Index Procedure- Edwards Cardioband System (Device group only)	Post- Edwards Cardioband System Procedure, Pre- Discharge (Device group only)	30 Day F/U (±7 days)	180 Day F/U (± 14 days)	1 Year F/U (±45 days)	2 Year F/U (± 60 days)	3, 4, 5 Year F/U (± 60 days)
Study Visit No.	1	3	4	5	6	7	8	9	10	11, 12, 13
Complete Blood Count (WBC, RBC, HCT, Hgb, platelet count)	Х		X				Х	Х		
Coagulation Panel (PT, PTT; INR for patients on vitamin-K antagonist)	X		Х							
Chemistry Panel (BUN, CO ₂ , Creatinine, Glucose, Cl, K, Na, AST (GOT), ALT (GPT), GGT, serum Total Protein, Albumin, Total Cholesterol, Triglycerides, HDL Cholesterol, Uric Acid)	X		X				X	Х		

PR

Test/ Assessment	Screening/ Baseline	Random -ization	Pre-Index Procedure- Edwards Cardioband System (Device group only; timing: per local institutional standard of care)	Index Procedure- Edwards Cardioband System (Device group only)	Post- Edwards Cardioband System Procedure, Pre- Discharge (Device group only)	30 Day F/U (±7 days)	180 Day F/U (± 14 days)	1 Year F/U (±45 days)	2 Year F/U (± 60 days)	3, 4, 5 Year F/U (± 60 days)
Study Visit No.	1	3	4	5	6	7	8	9	10	11, 12, 13
Cardiac biomarkers (troponins or CK/CK-MB)			X ²		X ²					
NT-Pro-BNP or BNP	X					Х	X	Х	X	Х
Modified Rankin Scale	X				X ³	X ₃	X ³	X ³	X ³	X ³
NIHSS	X ³				X ³	X ³	X ³	X ³	X ³	X ³
KCCQ	Х					Х	Х	Χ	Х	Х
SF-36	Х					Х	Х	Х	Х	Х
6 Minute Walk Test (6MWT)	Х					Х	Х	Х	Х	
Safety Primary Endpoint						Х				
Efficacy Primary Endpoint								Х		
Adverse Events	Х	Х	Х	Х	Х	Х	Х	Х	Х	Х
Clinical Frailty Scale [©]	Х									
Patient Preference Survey	Х									

PROTOCOL NUMBER: 2017-05

Test/ Assessment	Screening/ Baseline	Random -ization	Pre-Index Procedure- Edwards Cardioband System (Device group only; timing: per local institutional standard of care)	Index Procedure- Edwards Cardioband System (Device group only)	Post- Edwards Cardioband System Procedure, Pre- Discharge (Device group only)	30 Day F/U (±7 days)	180 Day F/U (± 14 days)	1 Year F/U (±45 days)	2 Year F/U (± 60 days)	3, 4, 5 Year F/U (± 60 days)
Study Visit No.	1	3	4	5	6	7	8	9	10	11, 12, 13
Activity Monitoring ⁴	Х	Х	X		X	Х	X	X		
Economic Data Collection ⁵			Х	Х	X					

⁽¹⁾ Perform pregnancy test prior to Cardiac CT, as required

⁽²⁾ Cardiac biomarkers: Collection for all patients undergoing Edwards Cardioband System implantation

⁽³⁾ If the patient experiences a stroke during the study, Neurological Assessments including NIH Stroke Scale (NIHSS) and Modified Rankin Scale should additionally be performed within 90 days from the date of the stroke by a neurologist, a neurology fellow, or designee.

⁽⁴⁾ Activity monitoring will be collected continuously from baseline to the 6 month visit. At 6 months if compliance is low an additional 1 month of monitoring will be issued. A month of continuous monitoring will be reinitiated at the 1 year follow-up visit.

⁽⁵⁾ Economic Data Collection will collect patient billing records for the index procedure.

All testing should be conducted at the investigational site to the extent possible. Follow-up testing may be performed at another site only if it is not possible for the patient (or the patient refuses) to return to the investigational site. In such cases, the Investigator may arrange for the study-required testing to be completed by the patient's local physician. However, it remains the responsibility of the study Investigator to ensure collection of appropriate information. Copies of source documents from the local physician must be obtained and kept in the patient's study file.

